### **8.2.3 Suspected Unexpected Serious Adverse Reactions**

An SAE that is also an unexpected adverse drug reaction is called a suspected unexpected serious adverse reaction (SUSAR). Unexpected adverse reactions are adverse reactions of which the nature or severity is not consistent with the applicable product information (eg, investigator's brochure for an unapproved investigational medicinal product or the Summary of Product Characteristics for an authorized medicinal product).

The Sponsor or its representative (eg, PRA if agreed to before start of the study) will promptly report (expedited reporting) the following SUSARs to the IEC:

- SUSARs that have arisen in the current clinical study that was assessed by the IEC

- SUSARs that have arisen in other clinical studies of the same Sponsor and with the same medicinal product, and that could have consequences for the safety of the subjects involved in the current clinical study that was assessed by the IEC

The Sponsor will promptly report (expedited reporting) all SUSARs to the CA and the Medicine Evaluation Board (MEB) of the country where this study is conducted and to the CAs in other Member States, as applicable.

SUSARs that have already been reported to the EMA Eudravigilance database do not have to be reported again to the CA and the MEB because they have direct access to the Eudravigilance database.

Expedited reporting will occur no later than 15 calendar days after the Sponsor or its representative has first knowledge of the adverse reactions. For fatal or life-threatening cases, the term will be maximally 7 calendar days for a preliminary report with another 8 days for completion of the report.

#### **8.2.4 Follow-up of Adverse Events**

Follow-up of AEs will continue until resolution, stabilization, or death. In case of ongoing AEs at database closure, the data obtained at database closure will be used in the statistical analysis. The follow-up of the AE will be documented in the source documents and will be described in the final CSR only if considered relevant by the Investigator.

#### **8.3 Pregnancy**

If the Investigator becomes aware of a pregnancy occurring in the partner of a male subject participating in the study up to 90 days after the last dose of study drug of the male subject, the pregnancy should be reported to the Sponsor within 1 working day of obtaining written consent from the pregnant partner. The Investigator may make arrangements for the partner to be counseled by a specialist, to discuss the risks of continuing with the pregnancy and the possible effects on the fetus. Monitoring of the partner should continue until the outcome of the pregnancy is known.

2.0 Introduction

This Statistical Analysis Plan (SAP) describes the statistical methods that will be used during the analysis and reporting of data collected under LMU Klinikum Protocol LMU-IMPH-BTZ-043-03.

This SAP should be read in conjunction with the study protocol and electronic case report form (eCRF). This version of the plan has been developed using the protocol dated 01-Jul-2021 (including all amendments and notes-to-files up to this protocol date) and the final eCRF(s) dated 15-Sep-21 (Screening) and 11-Oct-2021 (during Study).

An approved and signed SAP is a requirement for database lock.

This SAP covers the results that will be processed by the ICON/PRA Early Development Services (EDS) Biostatistics Department, and the results that will be processed by Nuvisan GmbH. ICON/PRA EDS will perform and is responsible for the safety and tolerability evaluation as well as for the total radioactivity in all matrices, including mass balance evaluation. Nuvisan will perform and is responsible for the pharmacokinetic (PK) evaluation of parent drug and main metabolite data in plasma and urine.

ICON/PRA EDS will prepare the Tables, Figures and Listings (TFLs) for Total Radioactivity (TR), BTZ-043 (M0), and main metabolites M1, M2, M4_{tot}, and M10.

Metabolic profiling (and Fe(%) of metabolites) is not part of this SAP and will be provided in a separate document.

This SAP supersedes the statistical considerations identified in the protocol; where considerations are substantially different, they will be so identified. Any post-hoc or unplanned analyses, or significant changes from the planned analysis in this SAP performed to provide results for inclusion in the clinical study report (CSR) but not included in this SAP, will be clearly identified in Section 9.8.2 of the CSR. Changes to planned analyses do not require an updated SAP but should be included in the CSR if significant.

3.0 Changes from Previous Version of Approved SAP

This is the first version of the SAP.

4.0 Study Objectives

4.1 Primary

- To determine the rates and routes of excretion of [¹⁴C]BTZ-043-related radioactivity, including mass balance of total drug-related radioactivity in urine and feces (and vomit, if applicable), following the oral administration of a single 500 mg dose of [¹⁴C]BTZ-043 in healthy male volunteers.
- To determine the pharmacokinetics (PK) of total radioactivity in blood and in plasma.
- To characterize the plasma PK of BTZ-043 and main metabolites by liquid chromatography-mass spectrometry (LC-MS), if applicable.
- To characterize the urine concentrations of BTZ-043 and main metabolites by LC-MS, if applicable.

4.2 Secondary

- To assess the safety and tolerability of a single 500 mg oral dose of BTZ-043 administered to healthy male volunteers.

4.3 Exploratory

- To identify BTZ-043's metabolites in plasma, and to quantify metabolites not measured in the primary objectives by radiometry in order to elucidate key biotransformation pathways and clearance mechanisms of BTZ-043 in humans.

- To identify BTZ-043's metabolites in excreta (urine and feces) and to quantify metabolites not measured in the primary objectives by radiometry in order to elucidate key biotransformation pathways and clearance mechanisms of BTZ-043 in humans.

5.0 Study Design

This study is a Phase 1, single-center, open-label study to investigate the absorption, metabolism, and excretion of BTZ-043 after a single oral administration of 500 mg BTZ-043 containing 3.7 MBq of [¹⁴C]BTZ-043 in 4 healthy adult male subjects.

A total of 4 evaluable subjects completing all procedures are required. Six (6) subjects will be enrolled in the cohort in order to have 4 evaluable subjects. If the cohort of 4 subjects administered with 500 mg BTZ-043 containing 3.7 MBq of [¹⁴C]BTZ-043 leads to less than 4 evaluable subjects, the 2 back-up subjects can be dosed subsequently to ensure that 4 subjects have completed all study procedures and are evaluable. If any of the 4 subjects vomits within 4 hours after study drug administration (approximately 2 times the median T_{max} of BTZ-043), the subject will be replaced.

Subjects will be admitted to the clinical research center on Day -1, which is the day prior to Day 1, the day of drug administration.

Subjects will receive a single oral dose of 500 mg BTZ-043 containing 3.7 MBq of [¹⁴C]BTZ-043 on Day 1. Subjects will be discharged from the clinical research center on Day 5 (approximately 96 hours after drug administration) upon satisfactory recovery of radioactivity. If the criteria for discharge are not met on Day 5, subjects will be required to remain confined for a maximum of 3 additional days (Days 6 to 8) until the criteria are met (daily check by quick counts or normal counts, as feasible). The in-house period should be prolonged up to the morning of Day 8 if at least 1 of the following applies:

- Total radioactivity in plasma is higher than 5% of radioactivity- C_{max} and/or PK parameters for determination of the total radioactivity-elimination phase cannot be determined reliably.
- The mass balance in urine and feces is not complete by Day 5 (i.e., <90%).
- The combined urinary and fecal excretion is not $\leq 1\%$ of the administered dose per 24 hours for 2 consecutive days based on ¹⁴C-radioactivity “quick counts” or normal counts, as feasible.

If the criteria for discharge are still not met on Day 8, subjects may be discharged from the clinical site upon discretion of the Investigator. To ensure that adequate consideration is given to the protection of the subject's interests, subjects with an incomplete mass balance on Day 8 will be asked to return to the clinical site for one or two 24-hour visits (Day 11-12 and Day 15-16).

The follow up assessments will be performed 30 days (± 2 days) after the [¹⁴C]BTZ-043 dose.

The schedule of assessments is shown in [Appendix 2: Schedule of Assessments](#)

5.1 Sample Size Considerations

Since the present study is a descriptive study aimed at assessing excretion routes of BTZ-043 by evaluating mass balance, a formal statistical sample size calculation was not performed. A sample size of 3 subjects is a minimum accepted number of subjects for AME studies and thus 4 subjects are considered sufficient to achieve the study objectives, even in case of one drop-out. Early termination subjects may be replaced if the total number of completers drops below 4, after mutual agreement between the Sponsor and ICON/PRA.

5.2 Randomization

This is an open label, non-randomized study.

5.3 Method of Assigning Subjects to Treatment Groups

After obtaining informed consent, subjects will be screened according to the inclusion and exclusion criteria. Subjects who meet all eligibility criteria receive a subject number upon inclusion in the study (Subject numbers 001-004). They receive the subject number just prior to dosing. The subject number ensures identification throughout the study. Replacement subjects will receive the number of the subject to be replaced, increased by 100 (eg, 101 replacement number for Subject Number 001), and will be administered the same treatment.

Subjects who drop out or withdraw for any reason without completing all screening evaluations successfully, are considered “screening failures”. Such subjects do not receive a subject number, and data will not be entered in the eCRFs.

6.0 Overview of Planned Analysis

6.1 Changes from Protocol

The protocol mentions a separate PK SAP. It has been decided to provide one integrated SAP, covering PK, safety and tolerability.

The protocol states in section 3.2 that four subjects are the minimum number of subject for AME studies. Although 4-6 subjects are preferred, AME data of three subjects are considered to be sufficient to achieve the study objectives.

6.2 Interim Analysis and Key

Interim analysis or TFLs before Database freeze (softlock) are not planned.

6.3 Final Analysis

Draft TFLs will be provided after database lock. After Sponsor comments have been incorporated, the TFLs will be finalized and incorporated in the first draft CSR.

7.0 Data Review

7.1 Data Management

Data handling and transfer will take place under the ICON/PRA Data Management Plan for the study.

7.2 Acceptance of Data for Summarization

Programming of analysis datasets and TFLs may be ongoing during the data management of the study. However, programming of analysis datasets and TFLs will be completed and quality controlled (QC'd) after database lock. Only quality assured (QA'd) results released by the Safety Laboratory, Bioanalytical Laboratory, or other external data source will be used for the programming of analysis datasets and TFLs for the final report. Any data values requiring investigation or corrections that are identified while programming the analysis datasets and TFLs will be sent to the project Data Manager. If the issue affects the TFLs the Programmer, Statistician (ICON/PRA EDS) or PK Analyst (Nuvisan) who identified the issue will follow it to resolution.

8.0 Definitions and General Analysis Methods

8.1 Analysis Data Presentation

8.1.1 Rounding

In listings, data will be presented with the same precision as the original data. Derived data will be rounded for presentation purposes.

Baseline, safety and tolerability data:

For all summaries, all descriptive statistics will be presented with the same precision (number of decimals) as the data they are calculated from. Percentages will be presented with one decimal.

The above rule can be applied directly to collected data. For derived data rounding will occur prior to summarization so a specific number of decimal places will have to be assumed to apply the above rounding rules for summary statistics.

PK concentration, parameters and total radioactivity data:

Derived PK parameters, except t_{max} , will be reported with a precision of 3 significant digits or as integers when the value is ≥ 1000 . The t_{max} will be reported with 2 decimals.

Any ratio will be rounded to one place beyond the decimal, no matter the value of the ratio.

Additional derived data will be rounded in the derived dataset as determined by the statistician.

8.1.2 Imputation

The following imputation will be performed:

- PK concentrations below the lower limit of quantification (LLOQ) (see 16.2.1)
- If the actual time or dose time is missing, the scheduled time may be substituted in order to calculate the PK parameters (see 16.2.2)
- Last observation carried forward (LOCF) for mass balance/ urine will be applied (see 16.2.3)
- missing period start or end date/times in Subject-level analysis dataset (ADSL), as appropriate.
- missing start or end date/times of adverse events (AEs) for the calculation of onset and duration (see 18.1.1)
- missing AE severity, relationship and seriousness of AEs (see 17.1.1)
- Laboratory data that are $< x$ or $> x$ (e.g. " <1.03 ", " >1000 ") will be imputed to x (respectively to 1.02 and 1001 in the example, see section 17.1.2).

Imputations / substitutions will be used in calculations and summaries only. Original data will be listed. If imputations / substitutions are listed, they will be listed along with the original data.

8.1.3 Descriptive Statistics

Unless otherwise indicated, continuous variables will be summarized with the following descriptive statistics: n (number of observations), (arithmetic) mean, standard deviation (SD), coefficient of variation (%CV, only for PK data), minimum (min) value, median, and maximum (max) value.

Categorical data will be summarized with frequencies and percentages. Percentages by categories will be based on the number of subjects exposed within a treatment.

For categorical data the categories will be presented in the tables exactly as they appear in the database.

8.1.4 Pooling

Not applicable for this SAP.

8.1.5 Unscheduled Measurements

Unscheduled measurements will be included in the listings. With the exception of unscheduled measurements used for baseline, unscheduled measurements will be excluded from the descriptive statistics and statistical analysis. In case an unscheduled measurement was performed immediately after the scheduled measurement because of a previous measurement error (e.g. equipment failure), this repeated measurement will be used, and the original erroneous measurement will be excluded from the analysis.

8.2 Analysis Data Definitions

8.2.1 Baseline Definition

Unless otherwise stated, baseline for post-dose evaluations is defined as the last observation recorded before the first study drug administration. The last observation can be an unscheduled / repeated measurement. If a pre-treatment observation is missing in a given period, then the screening value may be used.

8.2.2 Treatment/Subject Grouping

Label	Grouping
Study Drug	[¹⁴ C]-labeled BTZ-043
Treatment	500 mg BTZ-043 containing 3.7 MBq of [¹⁴ C]BTZ-043
Dose Level	500 mg

8.2.3 Common Variable Derivations

Variable	Data Type	Definition/Calculation
Change from Baseline	All	Post-dose Observation minus Baseline Observation
Analysis Study Day (Prior to Dose)	All	Date of Measurement minus Dose Date
Analysis Study Day (Post Dose)	All	Date of Measurement minus Dose Date +1
Relative Actual time from	Dosing	Actual time calculated as the sampling date/time minus IMP start of dosing date/time

8.2.4 QC

The analysis datasets and the TFLs will be QC'd according to the general ICON/PRA EDS QC plan.

8.2.4.1 Critical Data

The QC plan requires datasets be classified as critical or non-critical. Subject level, pharmacokinetic, and adverse events (ADSL, ADPC, ADPP, and ADAE) are considered as critical datasets. These datasets will be double programmed per the QC Plan.

8.2.5 ADaM Datasets and Metadata

The analysis datasets will be generated in accordance with Clinical Data Interchange Standard Consortium (CDISC) Analysis Data Model (ADaM) Version 2.1, and CDISC ADaM Implementation Guide 1.2. The following ADaM datasets will be prepared:

Table 1 ADaM Datasets

ADaM Dataset Name	Description	Double Programmed?
ADSL	Subject-Level Analysis Dataset	Yes
ADAE	Adverse Events Analysis Dataset	No
ADEG	ECG Analysis Dataset	No
ADLB	Laboratory Test Results Analysis Dataset	No
ADPC	Pharmacokinetic Concentrations Analysis Dataset	Yes
ADPP	Pharmacokinetic Parameters Analysis Dataset	Yes
ADVS	Vital Signs Analysis Dataset	No

A define.xml file version 2 with the corresponding metadata and Analysis Data reviewers guide (ADRG) will be included. Analysis results (analysis displays or program details) metadata are excluded from the define.xml.

8.3 Software

The statistical analysis and reporting will be done using SAS® for Windows™ Version 9.4 or higher (SAS Institute, Inc.).

PK parameter calculations will primarily be done using Phoenix® WinNonlin® (WNL) Version 7.0 or higher (Certara USA Inc.). For TR in plasma and blood, version 8.1 will be used. Additional PK computations may be performed in SAS®.

8.4 Statistical Methods

8.4.1 Statistical Outlier Determination

No statistical outlier analysis is planned.

8.4.2 Predetermined Covariates and Prognostic Factors

There are no predetermined covariates or prognostic factors.

8.4.3 Hypothesis Testing

No formal hypothesis testing will be done.

8.5 TFL Layout

Report layout will be according to the ICON/PRA EDS – ICH E3 compliant – CSR Template. The layout of Tables, Figures and Listings (TFLs) will be according to the ICON/PRA EDS standards.

No table shells will be provided. The TFLs will be provided in Adobe PDF format.

Format:

- Page size: A4
- Data in listings will be sorted by subject number and time point.

- Data in tables will be sorted by treatment and time point (where applicable).
- Column titles will be in title case letters.
- All tables and listings will be in landscape format.
- The following treatment label will be used in the TFLs: [14C]BTZ-043
 PK and mass balance TFLs will be presented with a subtitle for the analyte and specimen type, using BTZ-043, M1, M2, M4tot, M10 and Σ (BTZ-043, M1, M2, M4tot, M10) in plasma and urine, total radioactivity in plasma and blood, and total radioactivity excretion in urine/feces/vomit/sum of excreta.
 Σ (BTZ-043, M1, M2, M4tot, M10) will be reported as Sum (BTZ-043, M1, M2, M4tot, M10).

9.0 Analysis Sets

Analyses	Safety Set	Pharmacokinetic Set
Disposition Summaries		
Safety Assessments	✓	
Baseline Characteristics	✓	
Primary Analysis		✓
PK Concentrations		✓
PK Parameters		✓

9.1 Safety Set

The safety set will consist of subjects who receive one dose of [14C]BTZ-043. This set will be used for the safety data summaries, baseline characteristic summaries, and disposition summaries.

9.2 Pharmacokinetic Set

The PK set will consist of all subjects who receive the complete dose of [14C]BTZ-043 and have sufficient concentration-time data to calculate a valid C_{max} and AUC_{last} . Summaries of PK concentrations and summaries of PK parameters will be based on the PK set.

10.0 Subject Disposition

The number and percentage of subjects randomized, dosed, and members of each analysis set will be presented. The number and percentage of subjects who withdrew from the study prematurely and a breakdown of the corresponding reasons for withdrawal will also be presented.

11.0 Protocol Deviations

Protocol deviations will be listed by subject.

12.0 Demographic and Baseline Characteristics

12.1 Demographics

All demographic data as collected during the screenings visit will be listed by subject.

Subject demographics will be summarized descriptively for all subjects by treatment. The summary will include the subjects' age (in years), gender, race, ethnicity, weight at screening (in kg), height (in cm), and BMI at screening (in kg/m²). Demographics will be summarized for the safety set (and PK set if different from safety set).

12.2 Medical History

Medical history will be listed. Medical history will be coded according to Medical Dictionary for Regulatory Activities (MedDRA), version 24.1.

12.3 Other Baseline Characteristics

The results of drug and alcohol screen at screening will be listed.

The results of serology at screening will be listed.

The results of severe acute respiratory syndrome coronavirus 2 (SARS-CoV-2) polymerase chain reaction (PCR) tests will be listed.

Non-compliance to in- or exclusion criteria (if any) will be listed.

13.0 Concomitant Medications

Concomitant medications will be listed uncoded by subject. Medications with an end date prior to the first dose of study drug will be considered prior medications and will be noted in the listing. If a partial date allows a medication to be considered concomitant it will be categorized as such.

14.0 Treatment Compliance and Exposure

Exposure data will be listed by subject.

15.0 Pharmacokinetic Analyses

Due to the known instability of some BTZ-043 metabolites in native matrices, not every metabolite will be quantified by radio-profiling during this HAME study (stabilization measures are not compatible with radio-analysis sample processing). Instead, BTZ-043 and its main metabolites will be measured in plasma and urine samples by validated / qualified LC-MS methods applying appropriate stabilization measures, and all 'other metabolites' will be quantified by radio-profiling. For feces, such stabilization measures are not feasible, but labile metabolites are also expected to be of low priority/amounts, as anticipated from rat data. Therefore, quantitative PK feces data of BTZ-043 and its metabolites will come from radio-profiling solely.

Total radioactivity data and its PK evaluation will be generated as a separate report by ICON/PRA. An integrated PK evaluation will combine the metabolite quantification data from LC-MS measurements and radio-profiling for an overall evaluation of the drug's metabolic fate and excretion pathways, and compare these data with the total radioactivity data.

Note: The term 'other metabolites' in the following means all BTZ-043 metabolites, except the main metabolites M1, M2, M_{4total} and M10.

15.1 Pharmacokinetic Variables

PK concentrations will be collected in plasma, urine, and feces. If applicable - TR concentrations will be measured in vomitus.

15.1.1 Plasma Variables

15.1.1.1 Concentrations

- Individual plasma concentrations per time point for TR (reported in ICON/PRA TFLs + CSR).
- Individual plasma concentrations per time point for BTZ-043 (as measured by LC-MS, reported in ICON/PRA TFLs + CSR)
- Individual plasma concentrations per time point for metabolites M1, M2, M4_{tot} and M10 (as measured by LC-MS, reported in ICON/PRA TFLs + CSR)
- Sum of plasma concentrations per time point for BTZ-043 and its metabolites M1, M2, M4_{tot} and M10 (reported in ICON/PRA TFLs + CSR)
- Individual plasma concentrations per Hamilton AUC-pool for individual 'other metabolites' (as measured by radio-profiling – not a part of this SAP (reported in integrated PK report)

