CL/F	Apparent oral clearance, calculated as dose/AUC _{inf}	M0	CL/F from WNL
Vz/F	Apparent volume of distribution at terminal phase	M0	Vz/F from WNL

Note: AUCs will be calculated using linear up / log down, expressed in units of concentration (ng eq/mL) x time (h).

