15.1.3 Urine Variables

15.1.3.1 Amounts Excreted

- Individual cumulative amount of TR excreted in urine (Ae,urine). Reported in ICON/PRA TFLs + CSR.
 - Calculated as the urine volume times the urine concentration for each day pool and added up per subject.
- Individual cumulative amount of BTZ-043 (M0) excreted in urine (Ae,urine), as measured by LC-MS. Reported in ICON/PRA TFLs + CSR.
 - Calculated as the urine volume times the urine concentration for each day pool and added up per subject.
- Individual cumulative amount of M1, M2, M4_{tot} and M10, excreted in urine (Ae,urine), as measured by LC-MS. Reported in ICON/PRA TFLs + CSR.
 - Calculated as the urine volume times the urine concentration for each day pool and added up per subject.
- Individual cumulative amount of $\Sigma(M0, M1, M2, M4_{total}, M10)$, excreted in urine (Ae,urine). Reported in ICON/PRA TFLs + CSR.
 - Calculated as the urine volume times the urine concentration for each day pool and added up per subject.
- Inter-subject average cumulative amounts of individual 'other metabolites' in urine (Ae,urine), as measured by radio-profiling (see study protocol G-A-MET-21-002). Reported in integrated PK report.

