15.1.3.2 Parameters

- PK parameters for TR, BTZ-043 (M0), M1, M2, M4_{total}, M10, and $\Sigma(M0, M1, M2, M4_{total}, M10)$ as applicable, as defined in table 3. Reported in ICON/PRA TFLs + CSR
- PK parameters for 'other metabolites' and $\Sigma(M0$ and all metabolites), as applicable, as defined in table 3. Reported in integrated PK report.

Table 3: Urine Parameters

Parameter	Description	<Analyte	SAS Programming Notes
Aet (urine)	Total amount of drug/metabolites excreted into urine to time t, obtained by adding the amounts excreted over each collection interval per subject.	TR, M0, M1, M2, M4 _{total} , M10 and $\Sigma(M0, M1, M2, M4_{total}, M10)$	Summation t1-tn(Concentration (ng eq/mL)ti-t2*volume(mL)t1-t2)
Aet (urine)	Total amount of drug/metabolites excreted to time t, as obtained from one pool sample across all subjects covering $\geq 90\%$ of TR in urine.	Individual 'other metabolites', $\Sigma(M0$ and all metabolites)	n.a.
Fe (urine)	Fraction (%) of the administered dose excreted into urine $Fe = (Aet \text{ (urine)} / \text{Dose}) * 100$ per subject.	TR, M0, M1, M2, M4 _{total} , M10, $\Sigma(M0, M1, M2, M4_{total}, M10)$	Aet/500 mg*100

Parameter	Description	<Analyte	SAS Programming Notes
Fe (urine)	Fraction (%) of the administered dose excreted into urine Fe = (Aet (urine) / Dose) * 100, across all subjects.	Individual 'other metabolites', $\Sigma(M0 \text{ and all metabolites})$	n.a.
CL _R	Renal clearance of parent drug calculated as Ae/AUCinf	M0	Ae/AUCinf

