Concentrations of M0 and metabolites derived from metabolite profiling in Hamilton pool samples of individual subjects will be listed in the MetID and in the integrated PK report for the pooling interval. Plasma exposure of M0 and all metabolites (AUC_{0-t}) and %AUC_{0-t} of TR, M0 and metabolites will be calculated. Descriptive statistics (number of subjects, arithmetic mean, standard deviation) may be used to summarize the plasma concentrations and exposures across the 4 subjects for the pooling interval (if appropriate). The $\Sigma(M0, M1, M2, M3, M4, M10)$ as well as $\Sigma(\text{individual 'other metabolites'})$ may be listed (if appropriate).

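### Is the parent-plus-metabolite sum compared with total radioactivity in the wrong units, and is M3 counted twice?

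*SAP*

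**What the plan says.** SAP 15.1.1.1 lists plasma concentrations of BTZ-043 (M0) and of M1, M2, M4tot and M10, "as measured by LC-MS, reported in ICON/PRA TFLs + CSR", and then a "Sum of plasma concentrations per time point for BTZ-043 and its metabolites". SAP 15.1.3.1 gives one rule for the urine amounts of TR, M0, each main metabolite and the sum: "Calculated as the urine volume times the urine concentration for each day pool and added up per subject".

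Two places give units for these quantities:

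- The note under Table 1 (SAP 15.1.1.2) has plasma AUCs "expressed in units of concentration (ng eq/mL) x time (h"). It excepts no analyte.
- The programming note for the amount excreted in Table 3 (SAP 15.1.3.2) reads "Summation t1-tn(Concentration (ng eq/mL)ti-t2*volume(mL)t1-t2"). That row covers TR, M0, M1, M2, M4total, M10 and the sum. Fe (urine) is this amount over 500 mg, times 100.

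SAP 15.2.1 and Appendix 4 plot the sum on the same axes as TR. SAP 15.0 says that an integrated evaluation will combine the LC-MS and radio-profiling data "and compare these data with the total radioactivity data".

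On membership, the term 'other metabolites' "in the following means all BTZ-043 metabolites, except the main metabolites M1, M2", M4total and M10 (SAP 15.0). The closing paragraph of SAP 15.2.1, on the metabolite-identification and integrated PK reports, names a sum over "M0, M1, M2, M3, M4, M10" beside a sum of the 'other metabolites'. Both are optional there.

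**The concern.** An LC-MS assay measures the mass of the analyte it targets, whereas TR is expressed in parent equivalents. A metabolite heavier or lighter than the parent therefore contributes a different number on the two scales for the same number of molecules. The operations spelled out are to add, to multiply by volume and to divide by the parent dose. No molecular weight or factor appears in either document.

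If raw masses were used, the gap between the sum and TR would open or close for a reason unrelated to disposition, and a metabolite's Fe would not be a fraction of dose. That gap shows how much of the circulating and urinary radioactivity the main metabolites explain.

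M3 adds a second worry. Under the SAP 15.0 definition it is an 'other metabolite', yet SAP 15.2.1 puts it in the named sum too. Anyone adding the two sums would count it twice.

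**Working it through.** The plan states no figure to reproduce. The check compares the result in the stated units with the result if those units were ignored.

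**Inputs.** The dose is 500 mg and the unit is ng eq/mL (SAP Tables 1 and 3). Three quantities are not in the documents and are assumed: r, metabolite over parent molecular weight, 0.8 to 1.4; p, the parent's molar share of the sum, 0.2 to 0.8; and M3's share of the total, 1% to 20%.

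**1. In the stated units.** A concentration in ng eq/mL times a volume in mL gives ng eq. Suppose the total is 100 mg eq. Then Fe = 100/500 × 100 = 20%, a true fraction of dose. The sum is in the same unit as TR. Error: zero for any r.

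**2. With the label ignored.** Fe from raw mass = true Fe × r.

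- r = 0.8: 20 × 0.8 = 16%
- r = 1.4: 20 × 1.4 = 28%

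Apparent sum/TR = true sum/TR × [p + (1 − p) × r]. For a sum that truly explains 80% of TR:

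| p | r = 0.8 | r = 1.4 |
|---|---|---|
| 0.2 | 80 × 0.84 = 67.2% | 80 × 1.32 = 105.6% |
| 0.5 | 80 × 0.90 = 72.0% | 80 × 1.20 = 96.0% |
| 0.8 | 80 × 0.96 = 76.8% | 80 × 1.08 = 86.4% |

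These are outer limits, because each column puts all four metabolites at the same extreme ratio. Ratios on both sides of 1 would partly cancel.

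**3. What the conversion can reach.** For M0 the factor is 1, so its AUC, CL/F, Vz/F and renal clearance do not move. Excretion of TR in urine, feces and vomit, the total (SAP Tables 3 to 6) and the 90% recovery criterion for discharge use radioactivity only.

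**4. M3.** If the two sums in SAP 15.2.1 were added, a total that is truly 100% would read 100 + M3's share: 101%, 105%, 110% or 120% for shares of 1%, 5%, 10% or 20%. Neither document calls for that addition. The paragraph concerns plasma pools, so it has no route to Fe, which comes from urine and feces. The sum in the planned tables and figures (SAP 8.5, Appendices 3 and 4) has no separate M3 term. The two lists differ only in that M4total in one stands where M3 and M4 stand in the other. If M4total, which is not defined, covers M3, then M3 is not an 'other metabolite' and the overlap disappears. The documents do not settle this.

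**The case for a change.** The strongest case for a change is that a unit label is not a conversion rule. The label is applied to every analyte alike and may be shared template text: plasma Table 1 describes AUCinf in terms of blood concentration, with wording that matches the TR-only blood table. The work is also split. SAP 2.0 gives the LC-MS parent and metabolite evaluation to Nuvisan, and TR and all the tables and figures to ICON/PRA. With no table shells (SAP 8.5), each group could assume that the other converts. SAP 2.0 also places Fe of metabolites outside the SAP, while Table 3 defines it for the main metabolites. A missed conversion would not be obvious from the output, and a sentence would remove the doubt at almost no cost.

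Part of this stands. The factor is unwritten, M4total is undefined, and the scope statement and Table 3 do not agree. It does not show that raw mass will be used. Naming LC-MS identifies the assay, not the reporting unit, and where a unit is given it is an equivalent. Protocol 5.1.2 places the LC-MS work and the metabolite profiling under their own study protocols, G-A-LAB-21-004 and G-A-MET-21-002, where molecular weights and reporting units could be set out. Those are not available here, so their content is unknown. Silence in the SAP is not evidence that the step is omitted.

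**Conclusion.** The concern does not hold as an error in the plan. Reading the sum as unconverted mass goes against the units in SAP Tables 1 and 3, and in those units the sum and Fe are right. What remains is an unstated constant for each metabolite, a routine step that analysts reporting in ng eq would take. The 16% to 28% range for a true Fe of 20%, and the 72% to 96% range for a true 80% of TR at p = 0.5, apply only if the labels are disregarded. Both rest on an assumed weight ratio of 0.8 to 1.4.

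The M3 mismatch is real on the page but has no consequence for planned results. It sits in an optional listing, for reports separate from the planned tables and figures, and inflates a total only through an addition that nobody is told to make. Mass balance is untouched, and the comparison of the sum with TR is descriptive with no decision rule attached. A conversion note and a definition of M4total would help a reader, but they would not alter an analysis carried out in the stated units.
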